## 17.5. YP3A Inducers and CYP3A/P-gp Inhibitors

Prior to enrollment, strong CYP3A inhibitors, and moderate or strong CYP3A inducers are prohibited within 7 days of first dose of DS-3201b.

- Consumption of herbs/foods that may have an influence on PK of DS-3201b, such as star fruit, Seville orange or Seville orange-containing foods and beverages, and grapefruit or grapefruit-containing food or beverages, are prohibited from 3 days prior to the first dose of DS-3201b up to the last dose of DS-3201b.
- St. John's wort (hypericin) is not be permitted from 14 days prior to the first dose of DS-3201b up to the last dose of DS-3201b

During study participation, strong CYP3A inhibitors and/or P-gp inhibitors, if required for prophylactic administration for the treatment of symptoms such as infection, are permitted with a dose reduction of DS-3201b.

During study participation, moderate and strong CYP3A inducers are prohibited, as drugs having moderate or strong CYP3A inducing properties may decrease plasma DS-3201a concentrations and it is therefore necessary to avoid concomitant use of these drugs with DS-3201b. However, if medically essential to use as supportive care, concomitant use of moderate and strong CYP3A inducers is permissible after the first dose of the study drug. In this case, dose interruption of DS-3201b is not needed.

Please refer to the following links as well as to [Table 17.1](#):

PPD

**Table 17.1: List of CYP3A Inhibitors/Inducers and P-gp Inhibitors**

Please note that the following list of CYP3A inhibitor/inducers and P-gp inhibitors is not all-inclusive:

CYP3A/P-gp Inhibitors	CYP3A Inducers
Drugs having a strong CYP3A inhibitory effect and a P-gp inhibitory effect	Strong CYP3A inducers
clarithromycin	apalutamide
itraconazole	avasimibe
lopinavir and ritonavir	carbamazepine
ritonavir	enzalutamide
saquinavir and ritonavir	mitotane
telaprevir	phenytoin
tipranavir and ritonavir	rifampicin
	rifapentine
	St. John's wort
Strong CYP3A inhibitors	Moderate CYP3A inducers
boceprevir	bosentan
cobicistat	efavirenz
danoprevir and ritonavir	etravirine
elvitegravir and ritonavir	phenobarbital
grapefruit juice	primidone
idelalisib	rifabutin
indinavir and ritonavir	
ketoconazole	
mibepradil	
nefazodone	
nelfinavir	
paritaprevir and ritonavir and (ombitasvir and/or dasabuvir)	
posaconazole	
telithromycin	
troleandomycin	
voriconazole	
Moderate CYP3A inhibitors	Weak CYP3A inducers
aprepitant	armodafinil
ciprofloxacin	modafinil
conivaptan	rufinamide
crizotinib	
cyclosporine	
diltiazem	

CYP3A/P-gp Inhibitors	CYP3A Inducers

dronedarone erythromycin fluconazole fluvoxamine imatinib isavuconazole tofisopam verapamil
 
Weak CYP3A inhibitors
 
chlorzoxazone cilostazol cimetidine clotrimazole fosaprepitant istradefylline ivacaftor lomitapide ranitidine ranolazine ticagrelor
 
P-gp inhibitors (no strong CYP3A inhibition)
 
amiodarone carvedilol dronedarone lapatinib propafenone quinidine ranolazine verapamil
 
External medicine is excluded
	

CYP3A = Cytochrome P450 3A; P-gp = P-glycoprotein

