#### **1.4.3. Potential Risk of Drug-Drug Interaction**

In vitro, DS-3201a was metabolized extensively by CYP3A4 (approximately 66%) and CYP3A5 (approximately 30%), and to a lesser extent also by CYP2C8 (approximately 16%). The results of the in vitro study showed that DS-3201a is a substrate for P-gp. Drugs that are moderate-to-strong inducers of CYP3A4 may alter the PK of DS-3201a.

Study DS-3201-A-J104 demonstrated that the co-administration of itraconazole, a dual P-gp and strong CYP3A inhibitor, resulted in an approximately 4-fold increase in the AUCs and an approximately 3-fold increase in Cmax of DS-3201a. The co-administration of DS-3201b and the moderate CYP3A inhibitor fluconazole resulted in a 1.6-fold increase in the Cmax and AUCs of DS-3201a.

Additionally, the results of the DS3201-A-J104 study investigating drug interactions with CYP3A inhibitors and physiologically-based pharmacokinetic (PBPK) modeling analyses predicted that the combination of a single dose of DS-3201b and a strong CYP3A and P-gp inhibitor would increase the AUC of DS-3201a by approximately 4-fold, and a strong CYP3A inhibitor (no P-gp inhibitory effect) or a P-gp inhibitor (no CYP3A inhibitory effect) would

increase the AUC of DS-3201a by approximately 2-fold, respectively. If strong CYP3A inhibitors and/or P-gp inhibitors are co-administered, the dose adjustment guidance provided in [Table 3.1](#) must be followed. The increase in AUC of DS-3201a was less significant when DS-3201b was concomitantly administered with a moderate CYP3A4 inhibitor. Therefore, no dose reduction of DS-3201b is required when it is concomitantly administered with a moderate CYP3A inhibitor.

DS-3201a inhibited CYP3A4 (tested with midazolam,  $IC_{50}$  55.2  $\mu$ M) but did not directly inhibit CYP1A2, CYP2B6, CYP2C8, CYP2C9, CYP2C19, CYP2D6, or testosterone metabolism by CYP3A4. The potential DS-3201a inhibition on CYP3A4 (midazolam) was confirmed by subsequent determination of a  $K_i$  of 56.4  $\mu$ M. DS-3201a showed a tendency to be a metabolism-dependent inhibitor of CYP3A4, with an  $IC_{50}$  fold change of 7.8-fold. Determination of  $k_{inact}/K_i$  inactivation constants suggested that DS-3201a is not a potential CYP3A4 metabolism-dependent inhibitor, since the inactivation constants were not measurable. DS-3201a did not show metabolism-dependent inhibition of any other CYPs tested.

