### **3.2.3. DS-3201b Dose Reduction Guidelines**

The dose of DS-3201b will be reduced when concomitant strong CYP3A and/or P-gp inhibitors are co-administered (Table 3.1). When the strong CYP3A and/or P-gp inhibitors are discontinued, the subject will remain on the reduced dose for 3 days after the last dose of the inhibitor(s). After 3 days, the DS-3201b dose may be returned to the dose level that the subject was given before taking the inhibitor(s).

During this period of co-administration of moderate or strong CYP3A and/or P-gp inhibitors with DS-3201b, additional blood samples for PK analyses (total and unbound concentrations) should be collected (see Section 8 for additional details).

A list of CYP3A inhibitors/inducers and P-gp inhibitors is presented in Section 17.5.

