**Table 3.1: Criteria for Dose Reduction When Using Strong CYP3A Inhibitors and/or P-gp Inhibitors**

Drugs to be Co-administered with Care	Dose Adjustment Guideline	Examples of the dose reduction		
		When the Dose of the Study Drug is 500 mg Once Daily	When the Dose of the Study Drug is 250 mg Once Daily a	When the Dose of the Study Drug is 150 mg or 100 mg Once Daily a
Strong CYP3A inhibitors	Reduce DS-3201b dose to 50%	Reduce the dose of the study drug to 250 mg once daily	Reduce the dose of the study drug to 100 mg once daily	Reduce the dose of the study drug to 50 mg once daily
P-gp inhibitors	Reduce DS-3201b dose to 50%	Reduce the dose of the study drug to 250 mg once daily	Reduce the dose of the study drug to 100 mg once daily	Reduce the dose of the study drug to 50 mg once daily
Drugs having a strong CYP3A inhibitory effect and a P-gp inhibitory effect	Reduce DS-3201b dose to 25%	Reduce the dose of the study drug to 100 mg once daily	Reduce the dose of the study drug to 50 mg once daily	Interrupt the study drug

CYP3A = cytochrome P450 3A; P-gp = P-glycoprotein

a When the dose of study drug is 250 mg, 150 mg or 100 mg once daily, the Investigator should consult the Sponsor Medical Monitor before further reduction of the dose due to concomitant use of strong CYP3A or/and P-gp inhibitors

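### Table 17.1 puts verapamil and dronedarone in two inhibitor classes with different DS-3201b dose instructions, and the protocol does not say which instruction applies

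*Combined protocol and SAP*

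**What the plan says.** Table 17.1 (Section 17.5) sorts co-medications into classes. The class headed "P-gp inhibitors (no strong CYP3A inhibition" contains "amiodarone carvedilol dronedarone lapatinib propafenone quinidine ranolazine verapamil". The moderate CYP3A class ends with "dronedarone erythromycin fluconazole fluvoxamine imatinib isavuconazole tofisopam verapamil". Dronedarone and verapamil are in both.

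The two classes carry different dose instructions:

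- **Moderate CYP3A inhibitors.** Section 1.4.3 concludes that "no dose reduction of DS-3201b is required when it is concomitantly administered with a moderate CYP3A inhibitor". It reaches this after reporting a 1.6-fold rise in exposure with fluconazole.
- **P-gp inhibitors.** Section 3.2.3 states: "The dose of DS-3201b will be reduced when concomitant strong CYP3A and/or P-gp inhibitors are co-administered". The P-gp row of Table 3.1 reads "Reduce DS-3201b dose to 50" per cent. Section 1.4.3 also makes Table 3.1 mandatory for strong CYP3A and/or P-gp inhibitors.

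Table 3.1 has three rows: strong CYP3A, P-gp, and strong CYP3A with P-gp. Section 1.4.2 describes the trigger for reduction with *and*, where Sections 1.4.3 and 3.2.3 use *and/or*.

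On the exposure basis, Section 1.4.3 predicts that a strong CYP3A inhibitor without P-gp effect "or a P-gp inhibitor (no CYP3A inhibitory effect) would" raise AUC about 2-fold, and that an inhibitor with both effects would raise it about 4-fold.

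**The concern.** A site with a subject on verapamil can look the drug up in Table 17.1 and reach either of two instructions, each stated without exception. One leaves the dose unchanged and the other halves it. Two subjects in the same cohort on the same co-medication could therefore receive different DS-3201b doses, with neither site departing from the text.

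The modelling does not settle the matter. The 2-fold figure behind the 50% row is for P-gp inhibition with no CYP3A inhibition. The list to which that row is applied excludes only strong CYP3A inhibition. A moderate CYP3A inhibitor that also inhibits P-gp has no figure of its own.

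The timing matters for the dose-finding data. Exclusion criterion 8 and Section 5.2.1 bar strong CYP3A inhibitors before the first dose, but not moderate CYP3A or P-gp inhibitors. The overlap can therefore fall within Cycle 1, the DLT window. The logistic model in Section 11.11.1 relates DLT to dose, and no adjustment for inhibitor-altered exposure is described. For scale only, Section 11.11.3 limits predicted exposure increments between provisional doses to 30% to 100%. An unadjusted 2-fold ratio is already a 100% increase.

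**Working it through.** **Inputs, all from Section 1.4.3 and Table 3.1**

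- Moderate CYP3A inhibitor (fluconazole, observed): AUC ratio M = 1.6.
- P-gp inhibitor without CYP3A effect (model prediction): P = about 2.
- Strong CYP3A inhibitor without P-gp effect (model prediction): S = about 2.
- Strong CYP3A plus P-gp inhibitor (model prediction): about 4.
- Table 3.1 dose fractions: 50%, 50% and 25%.

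**Step 1: overlap of the lists.** Of the 14 moderate CYP3A inhibitors and the 8 P-gp inhibitors in Table 17.1, exactly two are shared: dronedarone and verapamil. Ranolazine is on the weak CYP3A list and the P-gp list. Neither Section 1.4.3 nor Table 3.1 gives a dose instruction for weak inhibitors, so ranolazine raises no conflict.

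**Step 2: reproduce the protocol's own figures.** Product rule: S × P = 2 × 2 = 4, as stated. An additive rule gives 1 + (2 − 1) + (2 − 1) = 3, which does not match. Dose fraction = 1 / AUC ratio: 1/2 = 50% and 1/4 = 25%, both as in Table 3.1.

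**Step 3: range for moderate CYP3A plus P-gp.** The protocol gives no figure, so three assumptions are shown. Residual exposure = dose fraction × AUC ratio. This takes exposure as proportional to dose, as the 1/ratio fractions in Table 3.1 do implicitly.

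| Assumption | AUC ratio | No reduction | Half dose |
|---|---|---|---|
| CYP3A effect contributes nothing | max(1.6, 2) = 2.0 | 2.0 × nominal | 1.0 × nominal |
| Additive | 1 + 0.6 + 1 = 2.6 | 2.6 × nominal | 1.3 × nominal |
| Product | 1.6 × 2 = 3.2 | 3.2 × nominal | 1.6 × nominal |

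**Step 4: the example doses in Table 3.1.** The half-dose column applies exactly at 500 mg (to 250 mg) and 100 mg (to 50 mg). The examples at 250 mg (to 100 mg) and 150 mg (to 50 mg) are fractions of 0.40 and 0.33. Across the three assumptions they leave 0.80 to 1.28 and 0.67 to 1.07 times nominal respectively.

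**The case against.** The strongest reply is that the rules can be read together. Section 1.4.3 makes Table 3.1 mandatory whenever a P-gp inhibitor is given, and Sections 3.2.3, 5.2.1 and 17.5 tie reduction to P-gp inhibitors with no exception for drugs that also inhibit CYP3A moderately. The heading of the P-gp list excludes only strong CYP3A inhibition, so moderate inhibitors can belong there. The no-reduction sentence would then concern the moderate CYP3A property alone. This reading is plausible, but the protocol nowhere states it, and the no-reduction sentence carries no exception either.

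There are also safeguards. Sections 3.2.3 and 8 call for total and unbound PK samples when moderate or strong CYP3A and/or P-gp inhibitors are given. The footnote to Table 3.1 asks for consultation with the Medical Monitor before a reduction at 250, 150 or 100 mg. The first measures exposure, and the second does not cover 500 mg. Neither tells a site which instruction governs.

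The scope is narrow, and this stands. Two drugs are affected. Dronedarone is also in Section 17.6 among the drugs to avoid, and Section 5.2.1 allows QT-prolonging drugs only when medically needed. No frequency of verapamil use is given.

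**Conclusion.** The protocol contains two stated dose rules that both apply to verapamil and dronedarone, with no precedence between them and no exposure prediction for their combined mechanism. Under the assumptions shown, exposure is 2.0 to 3.2 times nominal with no reduction and 1.0 to 1.6 times nominal at exactly half dose. The lower end assumes that these drugs produce the protocol's own 2-fold P-gp effect. The upper end extends a product rule inferred from one rounded example.

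A reader might infer more, and the documents do not support it:

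- *That neither instruction fits the predicted exposure of these drugs.* No such prediction exists. At the 2.0-fold floor, half dose restores nominal exposure exactly. At 3.2-fold it leaves 1.6-fold, the increase that Section 1.4.3 leaves unadjusted for fluconazole.
- *That exposure exceeds nominal under either instruction.* This fails at the same floor.
- *That the ratios translate into milligram equivalents of a higher dose.* That needs dose-proportional exposure in humans. Section 1.1.1.5.3 reports dose-proportionality only in rats and dogs.
- *That the MTD or RDE will be distorted.* Exposure altered in this way could enter the DLT data, but without a frequency of use the effect cannot be sized.

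**What to change.** The sponsor should reconcile Section 1.4.2, Section 1.4.3, Section 3.2.3, Table 3.1 and Table 17.1 so that every listed drug leads to exactly one instruction, with the trigger worded the same way throughout. The protocol should also state the exposure basis for drugs with both moderate CYP3A and P-gp inhibition, for example from the existing PBPK model. Which instruction prevails, what adjustment applies and which list a drug belongs on are for the sponsor to decide; none is proposed here.

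The cost is one clarification of protocol text and possibly one additional model run. No new visits or subjects are needed.

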## 17.6. Potential QT/QTc Prolonging Drugs

Concomitant drugs to be avoided during treatment with DS3201b.

The following list describes medications which prolong QTc interval.

This list should not be considered all-inclusive. Consult individual drug labels for specific information on a drug's propensity to prolong QTc interval.

Potential QT/QTc Prolonging Drugs	Generic Drug Name
Macrolide antibiotics	azithromycin erythromycin clarithromycin roxithromycin
Fluoroquinolone antibacterials	moxifloxacin ciprofloxacin gatifloxacin grepafloxacin levofloxacin sparfloxacin
Azole antifungals	fluconazole
Antimalarials	chloroquine halofantrine quinidine
Antiprotozoals	pentamidine
Antiemetics, gastrokinetics	droperidol ondansetron cisapride domperidone
Antipsychotics, antidepressants and other CNS agents	chlorpromazine cocaine citalopram donepezil escitalopram haloperidol ibogaine levomepromazine levomethadyl acetate levosulpiride methadone mesoridazine primozide

Potential QT/QTc Prolonging Drugs	Generic Drug Name
	propofol sevofluran sulpiride sultopride thioridazine
Antiplatelet agents	anagrelide cilostazol
Antihistamines	astemizole terfenadine
Antiarrhythmics, antihypertensives, antihyperlipidemics	amiodarone bepridil disopyramide dofetilide dronedarone flecainide ibutilide papaverine HCl probucol procainamide sotalol terlipressin terodilane

CCI

## 17.7. Highly Effective Methods of Birth Control

Female subjects of reproductive/childbearing potential with a male sexual partner must agree to use a highly effective form of contraception or avoid intercourse during and upon completion of the study and for at least 3 months after the last dose of study drug. For the purpose of this protocol, methods considered as highly effective birth control include:

- a. Combined (estrogen- and progestogen-containing) hormonal contraception associated with inhibition of ovulation (oral, intravaginal, or transdermal delivery).
- b. Progestogen-only hormonal contraception associated with inhibition of ovulation (oral, injectable, or implantable delivery).
- c. Intrauterine device (IUD).
- d. Intrauterine hormone-releasing system (IUS).
- e. Bilateral tubal occlusion.
- f. Vasectomized partner.
- g. Complete sexual abstinence.

Non-childbearing potential is defined as pre-menopausal with documented tubal ligation or hysterectomy; OR postmenopausal with documented  $\geq 12$  months of spontaneous amenorrhea (in questionable cases, a blood sample with simultaneous follicle-stimulating hormone [FSH]  $>40$  mIU/mL and estradiol  $<40$  pg/mL [ $<140$  pmol/L] is confirmatory). Females on hormone replacement therapy (HRT) and whose menopausal status is in doubt will be required to use one of the contraception methods outlined above for women of childbearing potential if they wish to continue their HRT during the study. Otherwise, they must discontinue HRT to allow confirmation of post-menopausal status prior to study enrollment. For most forms of HRT, at least 2 to 4 weeks must elapse between the cessation of therapy and the blood draw; this interval depends on the type and dosage of HRT. Following confirmation of their post-menopausal status, they can resume use of HRT during the study without use of a contraceptive method.

Female subjects must not retrieve ova or donate from the time of screening and throughout the study treatment period, and for  $\geq 3$  months after the final dose of study drug.

A male subject with a sexual partner who is a woman of childbearing potential must be willing and able to use a highly effective contraceptive method for the entire study treatment period and for  $\geq 3$  months after the final dose of study drug. Acceptable forms of contraception include condoms and highly effective contraception used by the usual female partner (see above for forms of highly effective contraception). Male subjects must not freeze or donate sperm starting at screening and throughout the study period, and  $\geq 3$  months after the final dose of study drug.

## 17.8. Schedule of Events

**Table 17.2: Schedule of Events Part 1 (Dose Escalation)**

Cycle (1 cycle = 28 days) (a)	Pre-Cycle							1							2							3			4 and beyond			Post-Cycle		
	Visit Number	1	2	3	4	5	6	7	8	9	10 and beyond	Visit Description	Screening	Exam and 1st Dose	Exam	Exam	Exam	Exam	Exam	Exam	EOT	EOS	F/U*	Exam	Exam	Exam	Exam	TBD	TBD	LTFU (q)
Cycle Day(s)	-14 to -1	1	2	8																										
Visit Window (days)																														
Time post-dose (hours)																														
Informed consent	X																													
SID number assigned	X																													
Demographics	X																													
Medical history	X																													
Inclusion/exclusion criteria	X																													
Pregnancy test (c)	X																													
Adverse events	X																													
Prior/concomitant medications	X																													
ECOG-PS	X																													
Height	X																													
Physical examination, including weight	X	X																												
Vital signs	X	X	X																											
Clinical laboratory (d)	X	X																												
Urinalysis (e)	X	X																												
TriPLICATE ECG (12-lead) (f)	X	X	X	X	X	X	X	X	X	X	X																			
Bone marrow assessment (h)	X											X																		
Biomarker blood sample (i)	X											X	X																	
DS-3201b administration (k)	X											X	X																	
Blood sample for DS-3201a PK (l)(m)	X	X	X	X	X	X	X	X	X	X	X	X	X	X	X	X	X	X	X	X	X	X	X	X	X	X	X			
Blood collection for histamine (n)	X	X	X	X	X	X	X	X	X	X	X	X	X	X	X	X	X	X	X	X	X	X	X	X	X	X	X			
Blood collection for protein binding determination (l)(m)	X	X	X	X	X	X	X	X	X	X	X	X	X	X	X	X	X	X	X	X	X	X	X	X	X	X	X			
Serum collection for AAG	X											X																		

Cycle (1 cycle = 28 days) (a)	Pre-Cycle								1								2								3								4 and beyond								Post-Cycle								LT FU							
Visit Number	1		2		3		4			5	6		7	8		9		10 and beyond																																						
Visit Description	Screening		Exam and 1st Dose		Exam		Exam		Exam	Exam	Exam		Exam		Exam		Exam		EOT Exam		EOS Exam		LT FU Exam																																	
Cycle Day(s)	-14 to -1		1		2		8			15	22		1	15		1		ND		ND		ND		ND																																
Visit Window (days)																																																								
Time post-dose (hours)		Pre-dose	0.5	1	2	4	6	8		Pre-dose	0.5	1	2	4	6	8																																								
Dispense DS-3201b										X	X								X	X	X	X	X	X	X	X	X	X	X	X	X	X	X	X	X	X	X	X	X	X	X	X														
Pill diaries dispensed/reviewed										X	X								X	X	X	X	X	X	X	X	X	X	X	X	X	X	X	X	X	X	X	X	X	X	X	X														
Medication compliance reviewed										X	X								X	X	X	X	X	X	X	X	X	X	X	X	X	X	X	X	X	X	X	X	X	X	X	X														
Optional marrow re-biopsy (o)																																																								
Reason for treatment discontinuation recorded																																																								
Survival status assessed																																																								
Unused meds & bottles collected																																																								
Subsequent AML/ALL treatments																																																								

a: Each cycle will last 28 days. Cohort safety assessment for DLTs will be performed after Day 28 of Cycle 1.

b: End-of-treatment visit will occur within 30 days after the last administration of DS-3201b. If the subject begins another form of anticancer therapy before the end of the 30 day period, every effort will be made to complete all the EOT assessments prior to commencing the new therapy. If there is an abnormality in need of monitoring beyond the EOT visit, subjects will be followed until resolution or confirmed stability of the abnormality.

c: Pregnancy test will be performed in female subjects of childbearing potential at screening, Cycle 3/Day 1, and EOT visit.

d: Clinical laboratory samples for Day 1 pre-dose (complete blood count with differential and absolute neutrophil counts, reticulocyte counts and peripheral blood blasts, serum chemistry, urinalysis, and coagulation profile) can be collected within 72 hours before the first dose. Creatinine clearance will be calculated at screening. Urinalysis will be performed for the indicated visits up to Cycle 3/Day 1 and at EOT visit.

e: Electrocardiograms will be performed pre-dose at Cycle 1/Days 1, 2, 8, 15, and 22, Cycle 2/Day 1, Cycle 3/Day 1, Cycle 4 and beyond/Day 1, and EOT, and additionally at 1, 2, 4, and 8 hours post-dose on Cycle 1/Days 1 and 8. Procedure window is  $\pm$  1 hour. Electrocardiograms will be performed in triplicate (5 minutes apart). Whenever there are time matched ECGs and PK sampling, ECGs should be done first. PK samples should be collected within 15 minutes of ECG collection.

f: If the ECG at 8 hours post-dose is not possible, then ECG may be performed at 6 hours ( $\pm$  10 minutes) post-dose.

g: All unscheduled bone marrow assessments of disease burden performed on non-visit days must be reported as unscheduled visits and samples for flow cytometry and/or mass cytometry, cytogenetics, and other biomarkers should be obtained.

i: Perform a bone marrow assessment if Cycle 2/Day 1 bone marrow revealed aplasia.

j: Blood samples drawn pre-dose at Cycle 1/Days 1, 2, 8, 15, and 22, Cycle 2/Day 1, and EOT visit for exploratory biomarker analysis.

k: DS-3201b is administered per protocol at the clinical site at the indicated time. Subjects should avoid food for 2 hours before and 1 hour after drug administration.

l: Blood samples for DS-3201a PK measurements and protein binding will be collected pre-dose at the indicated visits (Cycle 1/Days 1, 2, 8, 15, and 22, and Cycle 2/Day 1), at the indicated time points on Cycle 1/Days 1 and 8, and at EOT. Subjects will be instructed not to take their dose until after sample has been collected on clinic days. Additional samples will be collected at the indicated time points. The window for sample collection will be  $\pm$  15% of the specified time. Based on the PK profile established from the initial subjects treated in the study, sample collection time points may be modified upon notification by the Sponsor. Blood samples should be collected within 15 minutes of ECG collection on days with time matched ECGs and blood sampling.

m: If moderate or strong CYP3A and/or P-gp inhibitors are co-administered with DS-3201b, blood samples for DS-3201a PK measurements and protein binding should be collected on the first day of moderate or strong CYP3A and/or P-gp inhibitor dosing at pre-dose, 4 hours, and 8 hours post-dose of DS-3201b; and within 28 days after last day of moderate or strong CYP3A and/or P-gp inhibitor dosing at pre-dose, 4 hours, and 8 hours post-dose of DS-3201b.

n: Blood for histamine measurement will be obtained at the indicated time points (pre-dose and at 1, 2, and 6 hours post-dose on Cycle 1/Day 1 and pre-dose on Cycle 1/Days, 2, 8, and 15).

o: A bone marrow re-biopsy may be performed within 30 days of the last dose of DS-3201b in subjects who have achieved an initial complete remission/partial remission to DS-3201b by revised IWG response criteria or NCCN response criteria but later developed progressive disease while on therapy.

p: Based on the Investigator's clinical judgment, the frequency of bone marrow biopsies/aspirates can be reduced to once every 3 cycles after Cycle 3/Day1 until Cycle 12/Day1 (eg, Day 1 of Cycles 6, 9, and 12). After Cycle 12/Day1, the frequency of bone marrow biopsies/aspirates can be reduced up to once every 6 cycles (eg, Day 1 of Cycles 18, 24, etc).

q: LTFU will occur every 3 months after EOS Follow-up via telephone until death, loss to follow-up, or termination of study by the Sponsor.

r: Information on AML/ALL treatment (including stem cell transplants), HCT and HCT-relevant information (if performed), and response to treatment should be collected.

\* Note: The EOS Follow-up will occur 30 ( $\pm$  5) days after the last administration of DS-3201b. Follow-up information will be collected via a phone call or site visit. If the subject begins another form of anticancer therapy before the end of the 30 ( $\pm$  5)-day period, every effort will be made to complete all of the following EOS assessments prior to commencing the new therapy: assessment of AEs, current medications, subject survival status, and collection of any empty bottle(s) along with any unused medication.

AAG = alpha 1-acid glycoprotein; AML = acute myelogenous leukemia; CYP = cytochrome P450; DLT = dose-limiting toxicity; ECG = electrocardiogram; ECOG-PS= Eastern Cooperative Oncology Group – Performance Status; EOS = End-of-study; EOT = End-of-treatment; FU = follow-up; IWG = International Working Group; LTFU = Long-term Follow-up; NCCN = National Comprehensive Cancer Network; ND = not determined; P-gp = P-glycoprotein; PK = pharmacokinetics; SID = subject identification; TBD = to be determined.

